2.2. Endpoints

2.2.1. **Primary Endpoints**

Part 1:

The primary PK endpoints of LOXO-305 in plasma and total radioactivity in whole blood and plasma following oral administration of [¹⁴C]-LOXO-305 are as follows:

- area under the concentration-time curve (AUC) from time 0 extrapolated to infinity (AUC_{0-inf})
- AUC from hour 0 to the last measurable concentration (AUC_{0-t})
- maximum observed concentration (C_{max})
- t_{max}
- apparent terminal elimination half-life (t_{1/2})
- apparent systemic clearance (LOXO-305 only; CL/F)
- apparent volume of distribution (LOXO-305 only; V_z/F)
- AUC_{0-inf} of plasma LOXO-305 relative to AUC_{0-inf} of plasma total radioactivity (AUC_{0-inf} Plasma LOXO-305/Total Radioactivity Ratio)
- AUC_{0-inf} of whole blood total radioactivity to AUC_{0-inf} of plasma total radioactivity (AUC_{0-inf} Blood/Plasma Ratio).

The primary PK endpoints of total radioactivity in urine are as follows:

- amount excreted in urine (A_{eu})
- cumulative A_{eu}
- percentage of dose excreted in urine (f_{eu})
- cumulative f_{eu}.

The primary PK endpoints of total radioactivity in feces are as follows:

- amount excreted in feces (A_{ef})
- cumulative A_{ef}
- percentage of dose excreted in feces (fef)
- cumulative f_{ef}.

The primary outcome for metabolites will be derived:

- metabolic profile of LOXO-305
- identification of LOXO-305 metabolites.

Part 2:

The primary PK endpoints of LOXO-305 and total radioactivity in plasma following oral administration of LOXO-305 are as follows:

- AUC_{0-inf}, AUC_{0-t}, C_{max}, t_{max}, t_{1/2}, CL/F (LOXO-305 only), and V_z/F (LOXO-305 only)
- absolute bioavailability (F; LOXO-305 only).

The primary PK endpoints of $[^{14}C]$ -LOXO-305 in plasma following IV administration of $[^{14}C]$ -LOXO-305 are as follows:

- AUC0-inf, AUC0-t, Cmax, tmax, and t1/2
- total clearance (CL)
- Vz
- volume of distribution at steady state (V_{ss}).

The primary PK endpoints of [¹⁴C]-LOXO-305 and total radioactivity in urine collections are as follows:

- A_{eu}, cumulative A_{eu}, f_{eu}, cumulative f_{eu}
- renal clearance (CL_R; $[^{14}C]$ -LOXO-305 only).

The primary PK endpoints of [¹⁴C]-LOXO-305 and total radioactivity in feces collections are as follows:

• A_{ef}, cumulative A_{ef}, f_{ef}, cumulative f_{ef}.

Other PK parameters may also be reported.

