5.2. Study Treatment Administration

In Part 1, subjects will receive a single oral dose of 200 mg of [¹⁴C]-LOXO-305 (containing ~200 μ Ci) as an oral solution with 240 mL of room temperature water. In Part 2, subjects will receive a single oral dose of 200 mg LOXO-305 as 2 × 100-mg tablets with 240 mL of room temperature water followed 2 hours later by a single dose of < 100 μ g [¹⁴C]-LOXO-305 (containing ~1 μ Ci radioactivity [microtracer]) as an IV push over approximately 2 minutes. In both parts, an additional 100 mL of water may be administered if needed.

In Parts 1 and 2, oral dosing will be preceded by an overnight fast (ie, at least 10 hours) from food (not including water) and will be followed by a fast from food (not including water) for at least 4 hours post-oral dose. During Part 2, subjects may receive lunch approximately 2 hours after receiving the IV dose. Except as part of dose administration, subjects will restrict their consumption of water for 1 hour prior to oral dose and for 1 hour post-oral dose. At all other times during the study, subjects may consume water ad libitum.

Each unit dose will be prepared by qualified CRU staff. Each unit dose container will be appropriately labeled.

Appropriate unit dose(s), as described above, will be administered to subjects. Although the timing of events requires that each subject will be consistently administered the appropriate dose at a specific time, the exact dose time of subjects may be staggered to obviate the need to have all subjects on precisely the same study schedule. For each dose, the subject's actual dose time will be recorded in the source documents and transcribed into the eCRF.

Subjects will be instructed not to crush, split, or chew oral LOXO-305 tablets.

All oral doses will be administered while the subjects are seated and subjects will not be permitted to lie supine for 4 hours' post-oral dose except as necessitated by the occurrence of an AE(s) and/or study procedures. Subjects may be asked to be semi-supine/supine for the IV dosing.

Except when they are using the toilet, study subjects will be observed for approximately 4 hours post-oral dose to ensure that they are not experiencing AEs, becoming nauseated, or experiencing emesis.

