- j. Adverse events and SAEs will be collected beginning at informed consent. Adverse events will be recorded throughout the study (ie, from signing of the ICF until EOS, or until ET if the subject discontinues from the study and does not complete a follow-up phone call), either as subject medical history (if the event is reported as beginning prior to signing of the ICF or if the event occurs prior to study drug administration on Day 1 and is assessed as not related to study procedures by the Investigator [or designee]) or as AEs (if the event occurs after signing of

Protocol	CONFIDENTIAL
Covance Study: 8419667	Protocol Reference: LOXO-BTK-20007

the ICF but prior to study drug administration on Day 1 and is assessed by the Investigator [or designee]) as related to study procedures, or if the event occurs after study drug administration on Day 1 through EOT or ET regardless of relationship to study drug). From EOT or ET through EOS, only AEs assessed as related to study drug are to be recorded. All SAEs that develop from the time of ICF signing until EOS (or ET if the subject discontinues from the study and does not complete a follow-up phone call) are to be reported.

- k. A single oral dose of 200 mg of LOXO-305 as 2×100 -mg tablets followed 2 hours later by a single dose of $< 100 \ \mu g$ of [¹⁴C]-LOXO-305 (containing $\sim 1 \ \mu Ci$ of radioactivity [microtracer]) administered as an IV push over approximately 2 minutes.

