- 1. Blood samples for determination of LOXO-305 concentration (plasma) will be collected at the following timepoints relative to oral dosing: Prior to oral LOXO-305 dosing (within 30 minutes) and 0.5, 1, and 2 hours (just prior to IV dosing) after oral LOXO-305 dosing. Blood samples for determination of [¹⁴C]-LOXO-305 concentration (plasma) and total radioactivity (plasma) will be collected at the following timepoints relative to oral dosing: 2 hours (just prior to IV dosing) after oral LOXO-305 dosing. Blood samples for determination of LOXO-305 dosing. Blood samples for determination of LOXO-305 dosing. Blood samples for determination of LOXO-305 and [¹⁴C]-LOXO-305 concentration (plasma) and total radioactivity (plasma) will continue to be collected at the following timepoints relative to the start of IV [¹⁴C]-LOXO-305 dosing: 2 minutes (at end of IV), 10 minutes, 20 minutes, 45 minutes, and 1, 2, 3, 4, 6, 8, 10, 12, 24, 48, 72, 96, 120, 144, 168, and 192 hours postdose (Day 9 [EOT]), relative to the start of IV [¹⁴C]-LOXO-305 dosing (ie, start of LOXO-305 IV push). The allowed sampling window for blood samples for determination of LOXO-305 concentration (plasma) and total radioactivity will be the following: within 15 minutes prior to dosing (oral or IV) for the predose sample timepoint; ± 1 minute for sampling timepoints within the first 30 minutes; ± 5 minutes for sampling timepoints > 30 minutes < 12 hours; ± 30 minutes > 12 hours < 36 hours and ± 60 minutes for the sampling timepoints ranging from 48 to 192 hours.

- m. Urine samples for determination of [¹⁴C]-LOXO-305 and total radioactivity will be collected from 12 hours prior to oral dose administration (12 to 0 hours predose); from 0 (time of oral dose) to 4 hours postdose relative to the start of IV dose administration; from 4 to 8, 8 to 12, and 12 to 24 hours postdose relative to the start of IV dose administration; and for 24 hour intervals up to and including 192 hours postdose (Day 9 [EOT]), relative to the start of IV dose administration.

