## **8.5. Pharmacokinetic Assessments**

### **8.5.1. Pharmacokinetic Analysis**

Part 1 PK parameters will be determined where possible from plasma concentrations of LOXO-305 and whole blood and plasma concentrations of total radioactivity. Part 2 PK parameters will be determined from plasma concentrations of LOXO-305, plasma, urine, and feces concentrations of [C]-LOXO-305, and plasma concentrations of total radioactivity,

urine and feces concentrations of total radioactivity. Parameters will be determined using a model-independent approach performed using Phoenix WinNonlin (Certara USA, Inc.) version 8.1 or higher. Additional PK parameters beyond those listed in subsections below may be determined where appropriate.

PK analysis will be carried out using the actual dose administered (mg for oral doses and  $\mu$ g for IV dose) and actual blood sampling times postdose. If an actual time is missing, the sample concentration result will be treated as missing unless there is scientific justification to include the result using the nominal time. Calculation of PK parameters for urine and feces will be determined using nominal collection intervals.

In both parts, the whole blood and plasma parameters  $C_{max}$ ,  $t_{last}$ , and  $t_{max}$  will be obtained directly from the concentration-time profiles. If  $C_{max}$  occurs at more than 1 timepoint,  $t_{max}$  will be assigned to the first occurrence of  $C_{max}$ .

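### The Part 2 schedule labels the first IV sample as end-of-push but gives it a window that allows a draw before the push ends, which can lower the observed IV Cmax and shift tmax

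*Protocol*

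**What the plan says.** Footnote l to the Part 2 schedule (protocol Appendix 4) lists the first post-IV samples as "2 minutes (at end of IV), 10 minutes, 20 minutes, 45 minutes". It fixes the time origin as the beginning of the injection ("ie, start of LOXO-305 IV push"). Its window is plus or minus "1 minute for sampling timepoints within the first 30 minutes".

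Protocol section 5.2 and footnote k describe the IV dose as given "as an IV push over approximately 2 minutes". Neither gives a tolerance. Section 5.2 asks for the actual dose time to be recorded; it does not ask for the time at which the push ended.

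Protocol section 2.2.1 lists "AUC0-inf, AUC0-t, Cmax, tmax, and t1/2" among the Part 2 primary PK endpoints for [14C]-LOXO-305 after the IV dose, and SAP section 3.1 repeats them. The IV table in SAP section 8.5.1.2 derives Cmax and tmax for plasma total radioactivity from the same draws. Under SAP section 8.5.1, Cmax and tmax "will be obtained directly from the concentration-time profiles", and the analysis uses "actual blood sampling times postdose".

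**The concern.** One footnote gives two rules for the same sample. The label ties it to an event, the end of the push. The window ties it to a clock that starts with the push and allows 1 to 3 minutes. For a push of exactly 2 minutes, the first half of that window falls while drug is still going in. If a push runs a little over 2 minutes, a draw exactly on time is also early. Nothing says which rule governs, or that the draw must wait for the push to finish.

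The analysis cannot repair an early draw. Actual times place the concentration correctly on the time axis, but the value was still measured before the dose was complete, and no back-extrapolation is planned. The next sample is at 10 minutes. Without a recorded end of push, the analyst may be unable to tell which first samples were early. At stake are IV Cmax and tmax, which would then depend partly on push speed and draw timing.

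**Working it through.** The plan states no accuracy figure for IV Cmax, so there is none to reproduce. The check asks how far the reported Cmax falls below the end-of-push concentration.

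**Inputs from the documents.** Push time T of about 2 minutes; first sample at 2 ± 1 minutes from the start of the push; next sample at 10 minutes (protocol Appendix 4). Terminal half-life of about 20 h (protocol section 1.3.2, from oral data in patients), so β = ln 2/1200 per minute.

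**Assumptions, not in the documents.** Constant-rate push, instant mixing, and two-exponential disposition A·exp(−αt) + B·exp(−βt). Distribution half-life of 2, 5, 10 or 20 minutes. Initial-to-terminal ratio (A+B)/B of 3, 7 or 14. This gives 12 cases.

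**Formulas.** Each exponential term with coefficient X and rate k contributes (X/kT)·(1 − exp(−kt)) during the push. After the push, its value at T is multiplied by exp(−k(t − T)). Reported Cmax = max[C(first sample), C(10)]; loss = 1 − reported Cmax/C(T).

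**One case in full.** Take T = 2, distribution half-life 5 min (α = 0.1386) and ratio 7 (A = 6, B = 1).
- C(1) = (6/0.2773)(1 − 0.8706) + 0.500 = 2.80 + 0.50 = 3.30
- C(2) = (6/0.2773)(1 − 0.7579) + 0.999 = 5.24 + 1.00 = 6.24
- C(10) = 5.24 × 0.330 + 0.995 = 2.72
- Reported Cmax/C(2) = 3.30/6.24 = 0.53, a loss of 47%

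At the other end (20 min, ratio 3), C(1)/C(2) = 0.51 and C(10)/C(2) = 0.84. The 10-minute sample becomes Cmax, the loss is 16%, and tmax is 10 minutes.

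**All 12 cases.**

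| Push | First draw | Reported Cmax as share of end-of-push value | Loss |
|---|---|---|---|
| 2 min | 1 min | 53% to 84% | 16% to 47% |
| 2 min | 2 min | 100% | 0% |
| 2 min | 3 min | 74% to 98% | 2% to 26% |
| 3 min | 2 min | 69% to 86% | 14% to 31% |

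With a 2-minute push and a 1-minute draw, tmax moves to 10 minutes in 7 of the 12 cases.

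**Limits of the range.** With a single fast phase, C(1)/C(2) = 1/(1 + exp(−k)) and C(10)/C(2) = exp(−8k). The loss is greatest where these are equal, at a half-life of about 8.5 minutes: 1 − 0.52 = 48%. With one compartment and a 20 h half-life, C(10)/C(2) = 2^(−8/1200) = 0.995, a loss of 0.5%.

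**Effect on AUC and F.** Comparing a 1-minute with a 2-minute draw (2-minute push, linear trapezoid), IV AUC0-inf falls by 0.3% to 1.5% on the 12 cases. Because F has IV AUC0-inf in its denominator, F rises by a factor of at most 1/(1 − 0.015) = 1.015. Under wider assumptions (distribution half-life 1 to 15 minutes, slow-phase share 2% to 30%) the most extreme fall is about 4%, and 1/(1 − 0.04) = 1.04.

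**The case against.** The strongest reply is that the label already settles the matter. A draw at 1 minute of a 2-minute push is not at the end of the IV dose, so it fails the timepoint's own definition. The same footnote ties another sample to an event, the one just before IV dosing. The ±1 minute rule is generic and nothing says it overrides the label. This stands in part. A reader might infer that a mid-push draw is fully compliant, and the documents do not support that: it meets the window and breaks the label. What remains is a contradiction that site staff would have to resolve themselves.

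Second, collection procedures are deferred to a separate document and a laboratory manual (protocol section 7.1.1), and the eCRF is not available. Either may already carry the right instruction or a stop-time field. That is possible, but it does not alter the window the protocol states.

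Third, the size rests on assumed kinetics. The documents give no human IV distribution data, and rapid mixing is assumed for blood taken from the opposite arm. The upper figure needs both an early-edge draw and a fast distribution phase. A 3-minute push stretches the word approximately. All of this stands, which is why the result is given as a range with a lower limit near zero.

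Fourth, the endpoints are descriptive and no stated decision uses IV Cmax. That stands too. SAP section 8.1.1 provides for review of out-of-window samples before database lock, but a 1-minute draw is within the stated window and need not be picked up there.

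**Conclusion.** Footnote l contradicts itself and should be reconciled. For a 2-minute push sampled at 1 minute, observed IV Cmax would be 16% to 47% low on the stated assumptions, with tmax possibly at 10 minutes. The loss is under 1% if distribution is negligible. These figures describe a draw at the early edge of the window, not the expected result for every subject.

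The exposure is confined to IV Cmax and tmax for [14C]-LOXO-305 and for total radioactivity from the same draws; the size for total radioactivity was not modelled separately. A reader might infer that the absolute bioavailability result is in doubt. It is not: F is built on AUC0-inf (protocol section 8.3, SAP section 8.5.1.2), and the change there is about 0.3% to 1.5%, or about 4% at the extreme. A reader might also infer that one or two early samples among six would dominate the geometric CV. The documents give no between-subject variability for IV Cmax, so that cannot be shown.

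The point is worth correcting because two listed primary endpoints depend on it and the correction is cheap. Confidence is high in the contradiction and moderate in the size.

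**What to change.** In footnote l, make the end-of-push label govern. Draw the first sample immediately on completion of the IV push, never before it, with a one-sided window of 0 to +1 minute and as close to 0 as practical. Keep all later samples timed from the start of the push, as now. Record the actual start and end times of the push in the eCRF, so that the delay from end of push to first draw is known for each subject.

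The cost is the wording of one footnote and one extra time field; no sample is added. The downside is a tighter window for one draw. The change removes the mid-push error but not all timing sensitivity: a draw 1 minute after the end of a 2-minute push still loses 2% to 26% on the same assumptions. The recorded end time would make that loss interpretable.

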## LIST OF ABBREVIATIONS

Abbreviations pertain to the statistical analysis plan (SAP) only (not the tables, figures, and listings [TFLs]).

ADaM	analysis data model
AE	adverse event
$A_{ef}$	amount excreted in feces per sampling interval
$A_{eu}$	amount excreted in urine per sampling interval
AME	absorption, metabolism, and excretion
AUC	area under the concentration-time curve
$AUC_{0-\infty}$	area under the concentration-time curve from time 0 extrapolated to infinity
$AUC_{0-t}$	area under the concentration-time curve from time 0 to the last quantifiable concentration
BLQ	below the limit of quantification
CDISC	Clinical Data Interchange Standards Consortium
CK	creatinine kinase
CL	total clearance
CL/F	apparent total clearance
$CL_R$	renal clearance
$C_{\max}$	maximum observed concentration
CRU	Clinical research unit
CSR	clinical study report
CTCAE	Common Terminology Criteria for Adverse Events
ECG	electrocardiogram
EOS	end of study
EOT	end of treatment
ET	early termination
F	absolute bioavailability
$f_e$	percentage of dose excreted in urine and feces per sampling interval
$f_{ef}$	percentage of dose excreted in feces per sampling interval
$f_{eu}$	percentage of dose excreted in urine per sampling interval
Geom Mean	geometric mean
HYDF?	How Do You Feel?
$\lambda_Z$	apparent terminal elimination rate constant
LLOQ	lower limit of quantification
ln	natural log
LSM	Least squares mean
ICF	informed consent form

---

ICH	International Council for/Conference on Harmonisation of Technical Requirements for Registration of Pharmaceuticals for Human Use
IV	intravenous
MedDRA	Medical Dictionary for Regulatory Activities
MetID	metabolite profiling and identification
NC	not calculated
NR	no result
PK	pharmacokinetic(s)
SAE	serious adverse event
SAP	statistical analysis plan
SD	standard deviation
TEAE	treatment-emergent adverse event
TFL	table, figure, and listing
$t_{1/2}$	terminal elimination half-life
$t_{max}$	time to maximum observed concentration
UA	urinalysis
$V_{ss}$	volume of distribution at steady state
$V_z$	volume of distribution
$V_z/F$	apparent volume of distribution
WHODrug	World Health Organization Drug Dictionary

## 1. INTRODUCTION

This SAP has been developed after review of the clinical study protocol (Final Version 1.0 dated 29 June 2020) and electronic case report form.

This SAP describes the planned analysis of the pharmacokinetic (PK), and safety and tolerability data from this study. A detailed description of the planned TFLs to be presented in the clinical study report (CSR) is provided in the accompanying TFL shells document.

In general, the analyses are based on information from the protocol, unless they have been modified by agreement with Loxo Oncology, Inc. A limited amount of information about this study (eg, objectives, study design) is given to help the reader's interpretation. This SAP must be finalized prior to the lock of the clinical database for this study. When the SAP and TFL shells are approved, they will serve as the template for this study's CSR.

This SAP supersedes any statistical considerations identified in the protocol; where considerations are substantially different, they will be so identified. If additional analyses are required to supplement the planned analyses described in this SAP, they may be performed and will be identified accordingly in the CSR. Any substantial deviations from this SAP will be agreed with Loxo Oncology, Inc. and identified in the CSR.

This SAP is written with consideration of the recommendations outlined in the International Conference on Harmonisation (ICH) E9 guideline *Statistical Principles for Clinical Trials* and ICH E3 guideline *Structure and Content of Clinical Study Reports*.

The document history is presented in [Appendix 1](#).

## 2. STUDY OBJECTIVES

### 2.1. Primary Objectives

#### Part 1:

The primary objectives of Part 1 of the study are:

- to determine the mass balance and routes of elimination of [C]-LOXO-305 following oral administration of a single dose of 200 mg of [C]-LOXO-305 (containing ~200 µCi) in healthy male subjects
- to assess the PK of LOXO-305 following a single oral dose of [C]-LOXO-305
- to determine the whole blood and plasma concentrations of total radioactivity following a single oral dose of [C]-LOXO-305
- to determine urinary and fecal recovery of total radioactivity following a single oral dose of [C]-LOXO-305
- to characterize and identify metabolites of LOXO-305 in plasma, urine, and feces following a single oral dose of [C]-LOXO-305.

Part 2:

The primary objectives of Part 2 of the study are:

- to determine the absolute bioavailability of LOXO-305 following a single oral dose of 200 mg LOXO-305 along with an intravenous (IV) dose of < 100  $\mu$ g of [ $^{14}\text{C}$ ]-LOXO-305 (containing ~1  $\mu$ Ci of radioactivity [microtracer])
- to evaluate the PK of LOXO-305 and [ $^{14}\text{C}$ ]-LOXO-305 following oral dosing of LOXO-305 and IV dosing of [ $^{14}\text{C}$ ]-LOXO-305
- to evaluate the plasma concentration of total radioactivity following IV dosing of [ $^{14}\text{C}$ ]-LOXO-305
- to evaluate the urinary excretion of [ $^{14}\text{C}$ ]-LOXO-305 and total radioactivity following IV dosing of [ $^{14}\text{C}$ ]-LOXO-305
- to evaluate the fecal recovery of [ $^{14}\text{C}$ ]-LOXO-305 and total radioactivity following IV dosing of [ $^{14}\text{C}$ ]-LOXO-305.

**2.2. Secondary Objectives**

Part 1:

The secondary objective of Part 1 of the study is:

- to assess the safety and tolerability of [ $^{14}\text{C}$ ]-LOXO-305 when administered to healthy male subjects.

Part 2:

The secondary objective of Part 2 of the study is:

- to assess the safety and tolerability of LOXO-305 and [ $^{14}\text{C}$ ]-LOXO-305 when administered to healthy male subjects.

**3. STUDY ENDPOINTS**

**3.1. Primary Endpoints**

Part 1:

The primary PK endpoints of LOXO-305 in plasma and total radioactivity in whole blood and plasma following oral administration of [ $^{14}\text{C}$ ]-LOXO-305 are as follows:

- area under the concentration-time curve (AUC) from time zero extrapolated to infinity (AUC0-inf)
- AUC from time zero to the last quantifiable concentration (AUC0-t)
- maximum observed concentration (Cmax)

- time to maximum concentration ( $t_{max}$ )
- apparent terminal elimination half-life ( $t_{1/2}$ )
- apparent systemic clearance (LOXO-305 only; CL/F)
- apparent volume of distribution (LOXO-305 only;  $V_z/F$ )
- $AUC_{0-\infty}$  of plasma LOXO-305 relative to  $AUC_{0-\infty}$  of plasma total radioactivity ( $AUC_{0-\infty}$  Plasma LOXO-305/Total Radioactivity Ratio)
- $AUC_{0-\infty}$  of whole blood total radioactivity to  $AUC_{0-\infty}$  of plasma total radioactivity ( $AUC_{0-\infty}$  Blood/Plasma Ratio).

The primary PK endpoints of total radioactivity in urine are as follows:

- amount excreted in urine ( $A_{eu}$ )
- cumulative  $A_{eu}$
- percentage of dose excreted in urine ( $f_{eu}$ )
- cumulative  $f_{eu}$ .

The primary PK endpoints of total radioactivity in feces are as follows:

- amount excreted in feces ( $A_{ef}$ )
- cumulative  $A_{ef}$
- percentage of dose excreted in feces ( $f_{ef}$ )
- cumulative  $f_{ef}$ .

The primary outcome for metabolites will be derived:

- metabolic profile of LOXO-305
- identification of LOXO-305 metabolites.

